**Data Analysis:**

As this study is powered for cross-validation of the triage tool, aim 3 is exploratory in nature and may not detect a difference in validated disability metrics between the intervention control cohorts. Therefore, process improvement indicators will serve as the primary outcome measures for this aim, and disability and economic outcomes will be secondary outcomes. These results will let us calculate effect size for future prospective validation of the triage tool. Summary measures of all outcomes will be calculated using medians and interquartile ranges for numeric and ordinal variables and proportions for binary and categorical variables. Outcome metrics will be stratified by hospital site, injury severity, age, and economic indicators at each time point. Trends in physical and economic disability will be assessed over time. Process outcomes, disability measures, and disability distributions will be compared between baseline and intervention cohorts using Kruskal-Wallis one-way analysis of variance for numerical and ordinal variables and chi-square tests for categorical variables. Univariate linear regression and multiple regression adjusting for age, gender, mechanism, injury severity, and hospital site will be used to assess triage-tool contact as a predictor of GOSE disability

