## 2. STUDY AIMS

The primary study objectives are as follows:

**Aim 1: Establish the feasibility of using mobile phones to follow up on hospitalized trauma patients after discharge in Cameroon.**

*Hypothesis:* Mobile phones are a feasible way of contacting trauma patients after they are discharged from the hospital in Cameroon.

We will contact trauma patients discharged from four hospitals participating in the Cameroon National Trauma Registry at intervals of two weeks, one month, three months, and six months following discharge. The response rate and decay of response over time will be tracked.

**Aim 2: Cross-validate a telephone-based triage tool to identify trauma patients who would benefit from further medical care.**

*Hypothesis:* A triage tool administered over the telephone can effectively identify injured patients who would benefit from further care for their injuries.

An over-the-phone triage tool will be used to predict a binary outcome two-weeks after discharge: needs further care or does not need further care. An independent physician blinded to triage tool outcome who will also render a determination on the same binary outcome, will examine those patients contacted by telephone. Physician assessment will be used as the gold standard to calibrate the model, which will be validated in a separate patient cohort.

**Aim 3: Characterize the impact of timely follow-up on long-term disability and socioeconomic consequences associated with trauma in Cameroon.**

*Hypothesis:* Trauma patients in need of post-hospitalization medical care will have improved disability outcomes if follow-up care is delivered promptly.

Patients will be given a modified Glasgow Outcomes Scale-Extended (GOSE) survey to complete at two weeks, one month, three months, and six months after hospitalization to quantify the death and disability associated with traumatic injury for each patient. Pre- and post-intervention results will be compared.

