**Implementation/Data Collection:** Injured patients who are successfully contacted at any of the study time points following hospital discharge will answer an over-the-phone survey to assess disability using an augmented GOSE (aGOSE) instrument, which is a metric of multi-domain functional status initially targeted for patients following neurologic trauma. It has since been validated in diverse geographic locations and in broader clinical contexts. Additional questions to evaluate economic consequences of injury will be added to the existing GOSE instrument. As our preliminary experience indicates that respondents are extremely reticent to speak directly about money over the phone, indirect measures of economic consequences will be emphasized (**Table**). Respondents will also be asked whether they sought further care for their injuries and if so, whether care was rendered. Six months before we begin using the telephone triage tool we will collect baseline data at all 4 facilities, after which the triage tool will be implemented in a stepped-wedge fashion in the 4 facilities, staggered by three months for each facility's start date. The cohort of patients (or their surrogates) who answer the triage survey will also be asked to answer the aGOSE, which will be administered at 2-weeks and at 1, 3, and 6 months. This design will let us compare intervention patients with historical controls, while controlling for temporal trends.

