**Table: Examples of indirect measures of economic consequences**

1. Borrowing or selling household assets as a result of injury
2. Loss of household income as a result of the injury
3. Lost work by any member of the household as a result of the injury
4. Missed school by any member of the household as a result of the injury
5. Household food insecurity as a result of the injury
6. Any member of the household serving as a caregiver for the injured person.

level at 4 weeks, 3 months and 6 months after injury. Triage-tool contact will be evaluated for prediction of economic disability and presentation for follow-up care (both considered as binary variables) using univariate and adjusted multiple logistic regression.

**Outcomes:** Primary outcomes will include proportion of injured patients who seek clinical follow-up evaluation. Secondary outcomes will include GOSE disability level, work lost and other economic consequences of injury, such as spending savings and borrowing money.

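### Aim 3 is said to control for temporal trends, but no listed analysis names a calendar-time term, and the addendum that drops the stepped wedge gives no replacement analysis

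*Combined protocol and SAP*

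**What the plan says.** Section 3A, Aim 3, Implementation/Data Collection describes a six-month baseline at all four hospitals and a rollout staggered by three months, and concludes: "This design will let us compare intervention patients with historical controls, while controlling for temporal trends". Section 2 describes the same aim more plainly: "Pre- and post-intervention results will be compared".

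The Aim 3 Data Analysis lists three kinds of comparison:

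- Outcomes are "compared between baseline and intervention cohorts" with Kruskal-Wallis and chi-square tests.
- For GOSE level, univariate linear regression is used, and "multiple regression adjusting for age, gender, mechanism, injury severity, and hospital site will be used to assess triage-tool contact".
- "Triage-tool contact will be evaluated for prediction of economic disability and presentation for follow-up care", "using univariate and adjusted multiple logistic regression". No covariates are listed for these models. Presentation for follow-up care corresponds to the Aim 3 primary outcome.

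The same section calls Aim 3 exploratory and gives its results a further use: "These results will let us calculate effect size for future prospective validation of the triage tool".

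The addendum says the stepped wedge was abandoned because of the 2020 suspension, and puts its control of temporal trends in the conditional. It then revises the timeline and the Aim 2 sample size. It does not state how Aim 3 will be analysed instead.

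**The concern.** A staggered start makes calendar time separable from the tool, but only the analysis can remove it. If the model has site effects and no time term, intervention patients are on average later than baseline patients at the same site. Any calendar change in care-seeking, disability or response to calls then enters the tool coefficient.

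This matters more after the addendum. Baseline collection began in August 2019. The first site started the intervention in February 2020, and physician exams there had run for about one month when activities stopped. Implementation was then delayed at all sites, and work resumed in September 2020. Most of the contrast therefore spans the suspension. A difference that mixes the tool with that period would be carried forward as the effect size for a later study.

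**Working it through.** **1. Is calendar time named anywhere?** The plan gives no Aim 3 sample size, power or effect to reproduce, so the first check is of the text.

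| Aim 3 analysis | Covariates named | Calendar time |
|---|---|---|
| Kruskal-Wallis, chi-square | none possible | absent |
| Linear regression of GOSE, adjusted | age, gender, mechanism, injury severity, site | absent |
| Logistic regression (follow-up care, economic disability), adjusted | not listed | unnamed, not excluded |
| Trends in disability over time | no model given | describes outcomes; not tied to the tool contrast |

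**2. What does omitting time do on the planned layout?** The inputs are the Section 5 timeline grid (14 baseline and 12 intervention site-quarters). I assume equal cell sizes, independent errors, tool exposure equal to site phase, and no true effect. With site effects only, the tool coefficient for an outcome that drifts 1 unit per month is

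b = Σ w·g / Σ w, with w = n0·n1/(n0+n1),

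where g is the mean month of a site's intervention cells minus that of its baseline cells, and n0 and n1 are the numbers of baseline and intervention cells.

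| Site | n0, n1 | g (months) | w | w·g |
|---|---|---|---|---|
| 1 | 2, 3 | 3 − (−4.5) = 7.5 | 1.200 | 9.0 |
| 2 | 3, 3 | 6 − (−3) = 9.0 | 1.500 | 13.5 |
| 3 | 4, 3 | 9 − (−1.5) = 10.5 | 1.714 | 18.0 |
| 4 | 5, 3 | 12 − 0 = 12.0 | 1.875 | 22.5 |

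b = 63.0 / 6.289 = 10.02. With the one-year intervention phase given in the Figure 1 caption, the same formula gives 84.0 / 7.270 = 11.55. The unadjusted contrast carries 7.5 − (−1.71) = 9.2 months of drift. Adding period effects gives 0 in both layouts.

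Put as a conversion, a false 5-point difference in the proportion seeking care needs a drift of 5 / 10.02 = 0.50 points per month.

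A one-off change at all sites at month 3 passes through at 0.75 without time, 0.11 with linear time, and 0 with period effects.

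**3. What about the layout as run?** The documents do not give start dates for sites 2-4. One scenario that respects the February 2020 start at the first site is as follows, counting months from August 2019 = 0. The first site is in baseline in months 0-5 and on the tool in months 6-7 and 13-22. Sites 2-4 are in baseline in months 0-7 and on the tool in months 13-22. April-August 2020 is empty, and aGOSE recruitment stops in June 2021 as printed. The baseline end and tool start at sites 2-4 are assumed.

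- First site: g = 15.67 − 2.5 = 13.17, w = 6·12/18 = 4.00.
- Sites 2-4: g = 17.5 − 3.5 = 14.0, w = 8·10/18 = 4.444 each.
- b = (4.00·13.17 + 3·4.444·14.0) / (4.00 + 3·4.444) = 239.3 / 17.33 = 13.8.
- Step during the suspension: the first site has 10/12 = 0.833 of its tool months after it, the others all of them, so (4.00·0.833 + 13.33) / 17.33 = 0.96.

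If sites instead restarted one month apart from September 2020, the figures are 13.1 and 0.81; three months apart, 12.5 and 0.70.

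**4. What does the adjustment cost?** Compared with the site-only model, period effects multiply the standard error of the tool coefficient by 2.00 on the planned grid (2.05 with one-year phases). In the early-first-site scenario the factor is about 3.6, because the only overlap is two months at one site.

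**The case against.** The best reply is that the addendum has already withdrawn the promise. It repeats the Aim 3 sentence in the conditional and says the design was abandoned. The earlier sentence also credits the control to the design and does not promise a model term. Aim 3 is labelled exploratory, Section 2 openly describes a pre/post comparison, and period effects with four sites are expensive.

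Much of this stands. A reader might infer that the sponsor still claims full temporal control; the addendum does not support that. A reader might also infer that every Aim 3 model leaves time out. For the logistic models the documents are silent, and silence is not exclusion. Finally, a reader might infer that all sites switched together in September 2020, giving a pure before-after study. The addendum dates the first site's start to February 2020, and the dates for the other sites are not given.

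Three things survive. The cohort tests and the GOSE regression as listed do not adjust for time. No replacement Aim 3 analysis is stated. And neither the temporal-trends sentence nor the plan to derive a future effect size has been revised to match the addendum.

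**Conclusion.** The point holds and should be fixed, at a weight suited to an exploratory aim. Followed as written, the cohort tests and the GOSE model would count calendar change as a tool effect; for the logistic models the plan leaves this open. The multipliers (about 10 on the planned grid, about 13.8 with a step fraction of 0.96 in the early-first-site scenario) are conversions. They rest on equal cells, independent errors and partly assumed dates. They do not estimate bias in this trial, because no drift or step is documented and its direction is unknown. Whether period effects can be estimated at all depends on the actual phase dates: if baseline ended everywhere in February 2020 and sites 2-4 all started together, there may be no usable overlap.

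**What to change.** 1. Where sites were in different phases at the same calendar time, add calendar-period effects to all Aim 3 regressions, name them in the covariate list, and include the logistic model for presentation for follow-up care. Base Aim 3 conclusions on these models and not on the unadjusted tests.
2. If the actual start dates leave period effects not estimable, amend the Aim 3 temporal-trends sentence to agree with the addendum and label Aim 3 an uncontrolled before-after comparison. A model with linear calendar time may be given as a sensitivity analysis only, with a statement that it does not reliably remove a step change.
3. Do not carry a difference unadjusted for time forward as the effect size for a future study without that caveat.

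This needs wording and one set of covariates built from site start dates and call dates, which the study should already hold (an assumption). No new data are needed. The price is a weaker claim and wider intervals: about 2 times the standard error on the planned layout and about 3.6 times in the early-first-site scenario.

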**Exclusion Criteria:** No patients are excluded based on age, gender, or injury severity. If patients or their surrogate decision-maker do not give consent to participation, those patients will be excluded. According to the WHO definition above, the following will be excluded from the definition of "injury": "Whereas the above definition of an injury includes drowning (lack of oxygen), hypothermia (lack of heat), strangulation (lack of oxygen), decompression sickness or "the bends" (excess nitrogen compounds) and poisonings (by toxic substances), it does NOT include conditions that result from continual stress, such as carpal tunnel syndrome, chronic back pain and poisoning due to infections. Mental disorders and chronic disability, although these may be eventual consequences of physical injury, are also excluded by the above definition." Patients who are not formally admitted and discharged within 24 hours will be excluded.

**Implementation/Data Collection:** The trauma registry data are collected by a single trained research assistant in the emergency department of each hospital under the supervision of a field supervisor. Clinical staff verbally collect information on demographics, injury context, and mechanism from all traumatically injured subjects and/or an adult surrogate. They record this information on a paper trauma registry data collection form. Clinical staff also collect clinical data during patient care.

Each hospital's trained research assistants will then follow up with patients' progress to record complications, outcomes, and final disposition of patients during their time as an inpatient. They will collect trauma registry data collection forms daily from patient's hospital records and managing team and follow the hospital course of each patient that is admitted for further care. By participating in daily rounds, the research assistants will collect information on further treatment and outcomes, including complications and mortality. Research assistants will enter data into the encrypted, password-protected, online database hosted on REDCap ("Research Electronic Data Capture," which is a HIPAA-compliant, secure web application for building and managing online surveys and databases).

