## APPROACH

**Aim 1: Establish the feasibility of using mobile phones to follow up on hospitalized trauma patients after discharge in Cameroon.** This aim will be addressed through a prospective cohort study following discharged trauma patients longitudinally over 6 months. The following data will be extracted from the existing trauma registry: patient demographics, clinical course, injury severity, disposition, and patient cell phone numbers. All admitted trauma patients who provided cell phone numbers in the emergency department will be contacted at intervals of 2 weeks and 1, 3, and 6 months post-discharge. Contact points at 2 weeks and 1 month correspond with traditional post-injury follow-up visits when intervention is theoretically likely to positively impact patient trajectory. These time points have also been used in prior mobile-health follow-up studies in traumatic brain injury and surgical patients in developed settings. Three and 6-month time points were selected because our preliminary data showed higher rates of disability and survey response at 3 and 6 months than at 12 months. Attempts will be made to contact patients at least 3 times by calling and once by text message over a 1-week interval at each time point.

**Outcomes:** number and proportion of successful attempts.

[figure not shown]
**Sample Size:** This overall study is powered for Aim 2 (see below), but the study population for Aim 2 will be used to calculate the number and proportion of successful attempts in Aim 1.

**Data Analysis:** Feasibility will be assessed through calculation of the number of successful contacts; number of attempts required to achieve success; cost associated with personnel and telephone time; reason for contact failure; and survey administration time. Frequencies and proportions of successful contacts will be calculated for each time interval and temporal trends will be described. Mean and standard deviation for personnel time and call cost will be used to calculate average cost per patient contact and determine the overall feasibility of cell phone interviewing as a follow-up method.

**Aim 2: Cross-validate a telephone-based triage tool to identify trauma patients who would benefit from further medical care.**

**Study design:** The 4 hospitals will start in a stepped wedge design the implementation of mHealth telephone triage tool (see Figure 1).

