**Implementation/Data Collection:** Patients contacted two weeks after discharge will be asked to give additional consent for participating in the triage tool part of the study. Those who consent will be contacted by research assistants and will answer 7-question survey. Patients whose responses trigger concern about the need for further medical attention will be informed that they should return to care and given appropriate instructions. All patients, regardless of triaged status, will be asked to schedule a time for a physical exam and will undergo one either at the hospital or in their place of residence. If patients return to the hospital, compensation for travel expenses will be provided on a sliding scale. This exam will occur within 1 week of the phone interview. Trained study physicians will conduct a structured, standardized exam that will ultimately culminate in a dichotomous outcome for “needs further care” or “does not need further care”. Based on the exam, the physician will determine if the patient would benefit from further services (including additional follow-up care, diagnostic or therapeutic interventions). Additional data will be collected regarding physician opinion as to whether the patient is demonstrating on-trajectory recovery for their age, health status, and injury, and whether the patient is at high, moderate, or low risk for a poor outcome. At the 2-week and 6-month time points, all contacted patients will be asked about their satisfaction with formal medical services, post-injury follow-up care, perceived convenience, and utility of mobile telephone follow-up.

**Figure 1: Step-wedge design of study.** For each site: Diagonal lines depict a GOSE baseline data collection phase, gray arrows depict intervention phase (1 year/site), and black blocks depict follow-up phase (6 months/site).

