## ADDENDUM:

A pilot phase was started in July 2019 with actual recruitment for the study commencing in August 2019. Baseline data was collected from August 2019 using the aGOSE survey till February 2020 when the intervention phase commenced at the first site. New patients' recruitment for aGOSE data was stopped in June 2021 with 6-month follow-up completed by December 2022-January 2023.

The study's original research strategy included 3 hospitals. During the time from notice of award to receipt of funding and initiation of study procedures, approximately 14 months elapsed. This delay was in part due to the US PI moving institutions from UCSF to UCLA. During that time, the Cameroon Trauma Registry (CTR) Expanded from 3 hospitals to 4. Correspondingly, the mHealth study was implemented in all four hospitals included in the CTR (as indicated in the final study protocol).

Under the parent award, the intervention (a telephone-based triage tool) and associated follow-up physician exams were designed to be implemented in a stepped-wedge fashion at partner hospital sites, staggered by three months for each facility's start date. This step-wedge study design would have enabled us to compare intervention patients with historical controls, while controlling for temporal trends. However, research delays and interruptions due to the suspension of data collection activities at the peak of the COVID-19 pandemic in 2020 (April – September 2020) led us to discontinue this approach to maximize patient recruitment for the cross-validation of our triage instrument. We abandoned our original step-wedge study design in the revised research plan as it was no longer feasible to implement under the remaining study timeline and would incur unacceptable delays at the potential expense of instrument validation.

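### The Aim 3 adjusted GOSE model omits in-hospital complications and disposition, which the registry already holds and which are fixed before the triage call

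*Combined protocol and SAP*

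**What the plan says.** **The GOSE model.** Section 3A, Aim 3, Data Analysis specifies univariate linear regression and then an adjusted model: "multiple regression adjusting for age, gender, mechanism, injury severity, and hospital site will be used to assess triage-tool contact" as a predictor of GOSE level. Five covariates are named. The stratified summaries in the same section use site, injury severity, age and economic indicators, so they do not cover complications or disposition either.

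**The logistic models.** Economic disability and presentation for follow-up care are analysed "using univariate and adjusted multiple logistic regression". No covariates are named. Seeking follow-up care is the Aim 3 primary outcome; GOSE level is secondary.

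**What the registry supplies.** The Approach section, under Aim 1, extracts "patient demographics, clinical course, injury severity, disposition, and patient cell phone numbers". Under Implementation/Data Collection for the registry, research assistants "record complications, outcomes, and final disposition of patients during their time as an inpatient", and through daily rounds "the research assistants will collect information on further treatment and outcomes, including complications and mortality".

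**Timing and design.** Under Aim 2, Implementation/Data Collection: "Patients contacted two weeks after discharge will be asked to give additional consent for participating in the triage tool part of the study". Under Aim 3, Implementation/Data Collection: "This design will let us compare intervention patients with historical controls, while controlling for temporal trends". The Addendum then reports: "We abandoned our original step-wedge study design in the revised research plan".

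**The concern.** The Aim 3 contrast is not randomised. Patients exposed to the tool are compared with patients recruited under baseline collection, and the staggered rollout that was meant to separate the tool from time was given up. Covariate adjustment is most of the protection that remains.

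How the hospital stay went and how it ended plausibly predict later disability and care-seeking. Both are fixed at discharge, so the tool cannot have changed them and adjusting for them cannot remove any of its effect. The Approach section lists clinical course and disposition separately from injury severity, so the plan itself treats them as different information.

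There is a second possible route to imbalance. The exposure is triage-tool contact, which requires that the patient be reached and give a further consent. Both could depend on the course of the stay.

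At stake is the effect size that the Aim 3 Data Analysis section says will be carried into future validation work. Calling the aim exploratory explains low power. It does not make a removable bias harmless in a number meant for planning.

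**Working it through.** **1. The plan's own figure.** Aim 3 has no sample size, power, effect size or standard deviation to reproduce. The study is sized for Aim 2: 13 variables × 10 participants per variable ÷ 0.10 needing care = 1300, as stated. This point does not change that figure.

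**2. Covariates set side by side.**

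| Variable | In registry | Fixed before the two-week call | Named in GOSE model | Named in logistic models |
|---|---|---|---|---|
| Age, gender, mechanism, injury severity, site | yes | yes | yes | no list given |
| In-hospital complications | yes | yes | no | no list given |
| Disposition | yes | yes | no | no list given |

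The omission is explicit for GOSE. For the logistic models the covariate set is simply unstated.

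**3. Size in the GOSE model (all inputs assumed).**

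*Bias* = effect of a complication on GOSE × difference in complication share between cohorts.
- Low: 0.5 points × 0.05 = 0.025 points.
- High: 1.5 points × 0.10 = 0.15 points.
- No imbalance: zero.

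*Precision.* If the added covariates explain a further share R² of the variance left after the five listed ones, the standard error is multiplied by √(1 − R²), which is worth 1/(1 − R²) times as many patients. The power column assumes 650 per cohort, a difference of 0.3 GOSE points, SD 2 and two-sided 5%.

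| Further R² | SE multiplier | Equivalent sample | Power |
|---|---|---|---|
| 0 | 1.000 | 1.00 | 77.2% |
| 0.02 | 0.990 | 1.02 | not computed |
| 0.05 | 0.975 | 1.05 | 79.2% |
| 0.10 | 0.949 | 1.11 | 81.3% |
| 0.20 | 0.894 | 1.25 | 85.6% |

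**4. Size for care-seeking, if the logistic models used the same five covariates (assumed).** Let 30% seek care without a complication, let a complication multiply the odds by k, and let the tool have no effect. The share seeking care in a cohort with complication share c is 0.30(1 − c) + c·p, where p is the risk with a complication. With c = 20% in one cohort and 30% in the other:
- k = 2, p = 46.2%: 33.2% v 34.8%, a spurious difference of 1.6 points, odds ratio 1.08.
- k = 3, p = 56.3%: 35.3% v 37.9%, 2.6 points, odds ratio 1.12.
- k = 4, p = 63.2%: 36.6% v 39.9%, 3.3 points, odds ratio 1.15.

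Milder inputs (15% v 20% or 25%, k from 1.5 to 3) give apparent odds ratios of 1.02 to 1.12. None of these figures allows for the part already absorbed by severity, mechanism and site.

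**5. Precision in a logistic model.** The simulation used 800 replicates, 650 per cohort, 20% complications in both cohorts and a true odds ratio of 1.35. Adding the covariate raised the standard error of the log odds ratio from 0.1156 to 0.1169 (covariate odds ratio 2) and from 0.1137 to 0.1184 (covariate odds ratio 4). Power rose only from 71.8% to 73.3% and from 68.6% to 71.6%, because the estimate moved away from zero.

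**The case against.** The strongest case against is about reach, and much of it stands.

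- **A reader might infer that every Aim 3 adjusted model, including the one for the primary outcome, omits these variables.** The documents do not say so. The five-covariate list belongs to the linear GOSE model, a secondary outcome. For care-seeking and economic disability, the plan says only that the models are adjusted.
- **A reader might infer that adding the covariates narrows the interval for care-seeking.** It does not. The standard error of the log odds ratio rises slightly.
- **A reader might infer that the change repairs the damage done by the pandemic interruption.** It does not. No adjusted model contains calendar time, and complications and disposition do not stand in for it.
- **The sizes are all assumed.** Nothing in the documents shows that complications or irregular discharges differ between cohorts, and the five listed covariates already carry part of the case mix. The plan neither defines the severity measure nor says when it is taken, so it cannot be assumed to reflect arrival only.
- **The data may be uneven.** Complications are recorded during the stay at registry hospitals. Nothing says that the course at a receiving hospital is captured, and patients who leave early have a shorter record. Complications may therefore be under-recorded in just those disposition groups.

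These objections limit the point without removing it. The stated GOSE list still omits prognostic information that is available and precedes the tool, in a comparison with little other protection.

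**Conclusion.** The point holds for the adjusted GOSE model as written. For the logistic models, the fault is that the covariates are not stated.

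Under the assumed inputs, the consequence for GOSE is a bias of 0.025 to 0.15 points, and a standard error that adjustment would reduce by about 1% to 11%. The top of the bias range is half of the assumed 0.3-point difference (0.15 ÷ 0.3), but it takes the strongest inputs together and credits nothing to the existing covariates. For care-seeking, the possible bias under no tool effect is an odds ratio of about 1.02 to 1.15, and only if the model uses the same five covariates and the cohorts differ. If the cohorts are balanced on these variables, the bias is zero.

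Aim 3 is declared exploratory, and no stated sample size changes. This is a worthwhile refinement of the analysis, not a flaw that threatens the study.

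**What to change.** State one covariate set for all Aim 3 adjusted models: the five already listed, plus any in-hospital complication (yes/no) and disposition (routine discharge, left against medical advice, transferred). Apply it to GOSE, care-seeking and economic disability. For the logistic models, give less confounding as the reason, not precision.

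Before fixing the disposition levels, check how many patients in each category reach follow-up. The registry criteria include those who leave against advice, whereas the study's own inclusion sentence names admitted and transferred patients. Report how completely complications are recorded within each level.

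The cost is a sentence or two of analysis wording and about three parameters: one for complications and two for disposition. No new data collection is needed. The Addendum shows that recruitment has ended, so if analysis has begun, label the extended model post hoc or report it as a sensitivity analysis beside the five-covariate model. Say plainly that calendar-time confounding remains and needs its own treatment.
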